9.4.2 Main Analyses of Multiplicity-Controlled Secondary Endpoints

The statistical null hypothesis corresponding to the multiplicity-controlled secondary endpoints is that there is no difference between either upadacitinib 15 mg QD or 7.5 mg QD in combination with a 26-week CS taper regimen groups and the placebo in combination with a 52-week CS taper regimen group in terms of each multiplicity-controlled secondary endpoint.

Similar as the primary endpoint, for secondary binary endpoints, comparison will be made between each upadacitinib group and placebo group using CMH test for common risk difference estimated by a weighted average of risk differences across strata using the Mantel-Haenszel weights. Strata include stratification factors (Baseline CS dose [prednisone or prednisolone > 30 mg, prednisone or prednisolone ≤ 30 mg], and Baseline disease status [new onset disease, relapsing disease]). NRI-MI will be used as the primary approach to handle missing data except for the endpoint of proportion of subjects who experience at least 1 disease flare through Week 52. Point estimate, p-value, and 95% CI for the difference in proportions between each upadacitinib group and placebo will be provided.

For the endpoint of proportion of subjects who experience at least 1 disease flare through Week 52, the point estimate of flare rate at Week 52 from the Kaplan-Meier estimate for each stratum will be used to derive the stratified disease flare rate according to Sun R et al.² Point estimate, p-value, and 95% CI for the odds ratio between each upadacitinib group and placebo will be provided.

For continuous endpoints except for cumulative CS exposure, MMRM model will be used to compare each upadacitinib group and placebo. The Baseline and visit means will be presented for each treatment group who have both Baseline and post-baseline visit values. Point estimate, standard error (SE), and 95% CIs of LS mean change from Baseline within treatment groups along with p-value between each upadacitinib treatment group and placebo will be provided.

[figure not shown]

For cumulative CS exposure, which is likely non-normally distributed, van Elteren test stratified by stratification factors will be used. The median total cumulative CS exposure over the 52 weeks for each treatment group, p-value and the corresponding 95% CI (based on order statistics) for the median will be presented.

For the time to event endpoint (i.e., time to first disease flare), median time-to-event will be reported for each treatment group. Treatment comparisons in the distribution of time-to-event between each upadacitinib group and the placebo will be conducted using stratified log-rank test stratified by stratification factors. Median time for each treatment group will be provided based on Kaplan-Meier estimate. Subjects who never achieve the three criteria required before disease flare is considered (Section 9.4.1) during the treatment period will be censored at Baseline. Subjects who achieve the three criteria required before disease flare but never experience disease flare will be censored at the last assessment in Period 1. Analyses using Cox proportional hazards model with stratification factors as covariates will also be performed. Corresponding p-values, hazard ratios and 95% CIs will be reported.

For count endpoints (i.e., number of disease flare per subject and CS-related AEs), comparisons between each upadacitinib treatment group and the placebo group will be carried out using Poisson regression model with stratification factors as covariates, adjusted by the duration of study participation (or duration of study drug exposure for CS-related AEs). Log-transformation and robust standard error will be used in the Poisson regression model.

[figure not shown]
For all secondary binary endpoints (except for sustained complete remission and proportion of subjects who experience at least 1 disease flare), summary statistics will be provided for each treatment group using AO data. For all secondary continuous endpoints (except for cumulative CS exposure), an ANCOVA model will be applied based on AO data, with categorical fixed effects of treatment, stratification factors at randomization (Baseline CS dose [prednisone or prednisolone > 30 mg, prednisone or prednisolone ≤ 30 mg], and Baseline disease status [new onset disease, relapsing disease]), and the continuous fixed covariates of Baseline measurement (where applicable) in the model.

[figure not shown]
The attributes of the estimands corresponding to the multiplicity-controlled secondary efficacy objectives are summarized in Table 2.

Table 2. Summary of the Estimand Attributes Corresponding to the Multiplicity-Controlled Secondary Efficacy Endpoints

	Attributes of the Estimand					
Estimand Label	Treatment	Endpoint	Handling of Population Intercurrent Events		Statistical Summary	
Secondary binary endpoint (remission- related endpoints)	Upadacitinib vs. Placebo	Achievement of each binary endpoint at/by the defined timepoint	Subjects with GCA	 ICE1: composite Subjects will be considered as non-responders after ICE1. ICE3: hypothetical Data after ICE3 will be imputed by MI. 	Difference in proportion of subjects achieving each endpoin	
Secondary binary endpoint (proportion of subjects who experience at least 1 disease flare through Week 52)	Upadacitinib vs. Placebo	Proportion of subjects with at least 1 disease flare through Week 52	Subjects with GCA	 ICE1: treatment policy ICE3: treatment policy Data will be used regardless of ICE1 or ICE3. 	Difference in proportion of subjects with at least 1 disease flare through Week 52	
Secondary endpoint (rate of CS-related AEs)	Upadacitinib vs. Placebo	Rate of CS-related AEs by Week 52	Subjects with GCA	 ICE1: treatment policy ICE2: treatment policy ICE3: treatment policy Data will be used regardless of ICE1 or ICE2 or ICE3. 	Difference in the exposure adjusted treatment- emergent CS- related AE rate	

	Attributes of the Estimand					
Estimand Label	Treatment	Endpoint	Population	Handling of Intercurrent Events	Statistical Summary	
Secondary continuous endpoints (except for cumulative CS dose)	Upadacitinib vs. Placebo	Change from Baseline at Week 52	Subjects with GCA	 ICE1: treatment policy Data will be used regardless of ICE1. ICE2: hypothetical Data after ICE2 will be excluded and handled by MMRM ICE3: treatment policy Data will be used regardless of ICE3. 	Difference in the mean change from Baseline (or difference in the mean TSQM patient globa satisfaction subscale) at Week 52	
Secondary continuous endpoint (cumulative CS dose)	Upadacitinib vs. Placebo	Cumulative assessment by Week 52	Subjects with GCA	 ICE1: treatment policy ICE2: treatment policy ICE3: treatment policy Data will be used regardless of ICE1 or ICE2 or ICE3. 	Difference in cumulative assessment by Week 52	
Secondary count endpoint	Upadacitinib vs. Placebo	Number of disease flares per subject by Week 52	Subjects with GCA	 ICE1: treatment policy ICE3: treatment policy Data will be used regardless of ICE1 or ICE3 	Difference in the exposure adjusted number of disease per subject flares by Week 52	
Secondary time-to-event endpoint	Upadacitinib vs. Placebo	Time to first disease flare by Week 52	Subjects with GCA	 ICE1: treatment policy ICE3: treatment policy Data will be used regardless of ICE1 or ICE3. 	Difference in the median time to first disease flare by Week 52	

[figure not shown]

9.4.3 Sensitivity and Supplementary Analyses for Multiplicity-Controlled Secondary Efficacy Endpoints

For multiplicity-controlled secondary continuous endpoints (except for the endpoint of cumulative CS exposure), to assess deviations from MAR, tipping point analysis will also be conducted as additional sensitivity analysis. Details of the tipping point analysis are outlined in Appendix F. To assess the robustness of the main analyses, tipping point analyses will be conducted for cumulative CS exposure and proportion of subjects having at least one disease flare to handle missing data after premature discontinuation of study. For the comparison of cumulative CS exposure between each of the upadacitinib doses vs. placebo, the value at each visit after premature discontinuation from study will be imputed using a value within a range from the mean cumulative CS exposure of the same treatment group to the mean cumulative CS exposure of the other treatment group, with an increment of 10% difference between the two means. Van Elteren test will be conducted for each increment combination and the p-values will be summarized. For the comparison of proportion of subject having at least one disease flare between each of the upadacitinib doses vs. placebo, a proportion of the subjects who have prematurely discontinued from study and never had a disease flare will be imputed to have a disease flare. The proportion will start from 0% (AO) to 100% (NRI) with an increment of 10%. Given a set of increment combination, the subjects with missing response will be randomly assigned as responders or non-responders using binomial distribution to generate 30 imputed datasets, and CMH method will be performed on each of the imputed datasets to obtain the results for each comparison between the upadacitinib group versus the placebo group. SAS PROC MIANALYZE will be used to generate the final inferences using Rubin's rule.¹

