APPENDIX E. CORTICOSTEROID TAPERING SCHEDULE

	Blinded 5	2-Wk Costi	icosteroid*	Taper (Do	ose in mg)		Blinded 26-Wk Corticosteroid* Taper (Dose in ma								
Baseline	20	30	40	50	60	Baseline	20	30	40	50	60				
Wk 1	17	25	35	40	50	Wk 1	15	25	35	40	50				
Wk 2	17	20	30	35	40	Wk 2	12	20	30	35	40				
Wk 3	15	17	25	30	35	Wk 3	12	15	25	30	35				
Wk 4	15	17	20	25	30	Wk 4	10	12	20	25	30				
Wk 5	12	15	17	20	25	Wk 5	9	12	15	20	25				
Wk 6	10	15	17	17	20	Wk 6	8	10	12	15	20				
Wk 7	10	12	15	17	17	Wk 7	7	9	12	12	15				
Wk 8	10	10	15	15	17	Wk 8	6	8	10	12	12				
Wk 9	10	10	12	15	15	Wk 9	6	7	9	10	12				
Wk 10	9	10	10	12	15	Wk 10	5	6	8	9	10				
Wk 11	9	10	10	10	12	Wk 11	5	6	7	8	9				
Wk 12	9	9	10	10	10	Wk 12	4	5	6	7	8				
Wk 13	9	9	10	10	10	Wk 13	4	5	6	6	7				
Wk 14	8	9	9	10	10	Wk 14	3	4	5	6	6				
Wk 15	8	9	9	9	10	Wk 15	3	4	5	5	6				
Wk 16	8	8	9	9	9	Wk 16	2	3	4	5	5				
Wk 17	8	8	9	9	9	Wk 17	2	3	4	4	5				
Wk 18	7	8	8	9	9	Wk 18	1	2	3	4	4				
Wk 19	7	8	8	8	9	Wk 19	1	2	3	3	4				
Wk 20	7	7	8	8	8	Wk 20	0	1	2	3	3				
Wk 21	7	7	8	8	8	Wk 21	0	1	2	2	3				
Wk 22	6	7	7	8	8	Wk 22	0	0	1	2	2				
Wk 23	6	7	7	7	8	Wk 23	0	0	1	1	2				
Wk 24	6	6	7	7	7	Wk 24	0	0	0	1	1				
Wk 25	6	6	7	7	7	Wk 25	0	0	0	0	1				
Wk 26	5	6	6	7	7	Wk 26	0	0	0	0	0				
Wk 27	5	6	6	6	7	Wk 27	0	0	0	0	0				
Wk 28	5	5	6	6	6	Wk 28	0	0	0	0	0				
Wk 29	5	5	6	6	6	Wk 29	0	0	0	0	0				
Wk 30	4	5	5	6	6	Wk 30	0	0	0	0	0				
Wk 30	4	5	5	5	6	Wk 30	0	0	0	0	0				
Wk 32	4	4	5	5	5	Wk 32	0	0	0	0	0				
Wk 33	4	4	5	5	5	Wk 33	0	0	0	0	0				
		4	4	5	5		0	0	-	0	0				
Wk 34 Wk 35	3	4	4	4	5	Wk 34 Wk 35	0	0	0	0	0				
Wk 36	3	3	4	4	4	Wk 36	0	0	0	0	0				
Wk 37	3	3	4	4	4		0	0	0	0	0				
Wk 38	2	3	3	4	4	Wk 37 Wk 38	0	0	0	0	0				
Wk 39	2	3	3	3	4	Wk 39	0	0	0	0	0				
Wk 40	2	2	3	3	3	Wk 40	0	0	0	0	0				
Wk 41	2	2	3	3	3	Wk 40	0	0	0	0	0				
Wk 42	1	2	2	3	3	Wk 41	0	0	0	0	0				
		2	2	2	3		0			0	_				
Wk 43 Wk 44	1 1	1	2	2	2	Wk 43 Wk 44	0	0	0	0	0				
	1	1	2	2	2		0	0		0	0				
Wk 45				2	2	Wk 45	0	0	0	0	0				
Wk 46 Wk 47	0	1	1	1	2	Wk 46 Wk 47	0	0	0	0	0				
	-						-	-	-	-	_				
Wk 48	0	0	1	1	1	Wk 48	0	0	0	0	0				
Wk 49	0	0	1	1	1	Wk 49	0	0	0	0	0				
Wk 50	0	0	0	1	1	Wk 50	0	0	0	0	0				
Wk 51	0	0	0	0	1	Wk 51	0	0	0	0	0				
Wk 52	0	0	0	0	0	Wk 52	0	0	0	0	0				
			til 20 mg												

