2.3 Treatment Assignment and Blinding

The study duration includes a 35-day maximum screening period; a 52-week randomized, double-blind, parallel-group treatment period (Period 1); a 52-week blinded extension period in which subjects who qualify are either re-randomized or continue on their original assignment (Period 2); and a 30-day follow-up period.

In Period 1, subjects who meet eligibility criteria are randomized in a 2:1:1 ratio to 1 of 3 treatment groups:

- Upadacitinib 15 mg administered daily + 26-week CS taper regimen
- Upadacitinib 7.5 mg administered daily + 26-week CS taper regimen

[figure not shown]
Placebo administered daily + 52-week CS taper regimen

Randomization of all subjects, except for those in Japan, will be stratified by Baseline CS dose (prednisone or prednisolone \geq 30 mg, prednisone or prednisolone \leq 30 mg), prior use of an IL-6 inhibitor (yes, no), and Baseline disease status (new onset disease, relapsing disease). In Japan, the study will attempt to include a minimum of 8 subjects. No stratification will be utilized for randomization, however, data on all three stratification factors will be collected for all Japanese patients.

Starting at Baseline, all subjects will switch from CS obtained outside of the study to open-label oral prednisone or prednisolone provided by the Sponsor at a dose of 20, 30, 40, 50, or 60 mg QD. The initial dose of prednisone or prednisolone will be at the discretion of the investigator, based on disease severity and comorbid medical conditions. Prednisone or prednisolone will be tapered according to a predefined schedule over a 26- or 52-week period. Open-label prednisone or prednisolone will be provided until the dose is tapered to 20 mg/day. Subsequently, blinded prednisone or prednisolone will be provided for the remaining blinded taper regimen through Week 52. Additional details regarding CS therapy during the study can be found in Section 5.8 of the protocol.

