[figure not shown]
For the primary analysis of the secondary continuous efficacy endpoints (except for cumulative CS exposure), estimands with treatment policy and hypothetical strategy to handle ICEs will be used: data collected will be used regardless of ICE1 or ICE3. Data collected after ICE2 will be excluded and missing data will be handled by mixed effect model repeat measurement (MMRM).

For the primary analysis of secondary endpoint of cumulative CS exposure, estimand with treatment policy strategy to handle ICEs will be used: data collected will be used regardless of ICE1, ICE2, or ICE3.

For the primary analysis of secondary time-to-event endpoint (i.e., time-to-first disease flare), estimand with treatment policy strategy to handle ICEs will be used: data will be used regardless of ICE1 or ICE3. ICE2 is not applicable for the endpoint of time-to-first disease flare.

For the primary analysis of secondary count endpoint (i.e., number of disease flares per subject), estimand with treatment policy strategy to handle ICEs will be used: data will be used regardless of ICE1 or ICE3. ICE2 is not applicable for the endpoint of number of disease flares per subject.

For the primary analysis of the secondary efficacy endpoint of rate of CS-related AEs, estimand with treatment policy strategy to handle ICEs will be used: data collected will be used regardless of ICE1, ICE2, or ICE3.

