12.0 Overall Type-I Error Control

The overall Type I error rate of the primary and the multiplicity-controlled secondary endpoints will be strongly controlled using a graphical multiplicity adjustment method.^{3,4}

Specifically, the primary and multiplicity-controlled secondary endpoints as specified in Section 3.1 and Section 3.2 will be tested in the order as specified below and will begin with testing the primary endpoint for upadacitinib 15 mg dose using α of 0.05. Continued testing will follow a pre-specified α transfer path which includes downstream transfer along the endpoint sequence within each dose as well as cross-dose transfer. Adjusted P values for the primary and multiplicity-controlled secondary endpoints will be provided based on the testing procedure.

The testing procedures are provided below in Figure 2 (for US/FDA regulatory purpose) and Figure 3 (for PMDA regulatory purpose). The arrows specify the α transfer paths. Once a null hypothesis of an endpoint is rejected (i.e., deemed significant) at its assigned significance level, its significance level will be transferred to subsequent endpoint(s) following the arrow(s). The numbers on the arrows denote the weights for transferring and (possibly) splitting significance levels. Specifically, the weight 1 and 1/2 denotes 100% and 50% transfer of significance level, respectively. The primary and multiplicity-controlled secondary endpoints (V1-V7 in Table 3) will be tested sequentially. The remaining multiplicity-controlled secondary endpoints will be grouped together (V8-H in Table 3) and tested using Hochberg procedure.

[figure not shown]

Table 3. List of Primary and Secondary Endpoints for Regulatory Purpose (FAS1)

Name	Variable			
V0	Proportion of subjects achieving sustained remission at Week 52			
V1	Proportion of subjects achieving sustained complete remission from Week 12 through Week 52			
V2	Cumulative CS exposure through Week 52			
V3	Time to first disease flare through Week 52			
V4	Proportion of subjects who experience at least 1 disease flare through Week 52			
V5	Proportion of subjects in complete remission at Week 52			
V6	Proportion of subjects in complete remission at Week 24			
V7	Change from Baseline in the 36-item Short Form Quality of Life Questionnaire (SF-36) Physical Component Score (PCS) at Week 52			

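### The tipping-point analysis for cumulative steroid exposure can impute a total below the dose a withdrawn subject has already received

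*SAP*

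**What the plan says.** Cumulative CS exposure is V2 in SAP Table 3, the second of the multiplicity-controlled secondary endpoints. Under SAP 8.0 it follows a treatment-policy strategy: "data collected will be used regardless of ICE1, ICE2, or ICE3". SAP 9.2 analyses it as observed, without imputation.

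SAP 9.4.3 adds a tipping-point analysis for subjects who leave the study. In it, "the value at each visit after premature discontinuation from study will be imputed using a value within a range". One end of that range is set by the subject's own group: the value is "imputed using a value within a range from the mean cumulative CS exposure of the same treatment group". The range then runs "to the mean cumulative CS exposure of the other treatment group, with an increment of 10% difference between the two means". Finally, "Van Elteren test will be conducted for each increment combination and the p-values will be summarized".

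The section does not say that the recorded dose is a floor, that only the later increment is imputed, or that the means are specific to starting dose or stratum. SAP Appendix F, which details the tipping point for the other continuous endpoints, excludes this one in its title. Appendix H adds nothing on it.

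**The concern.** A cumulative dose can only rise. SAP 2.3 has CS "provided by the Sponsor at a dose of 20, 30, 40, 50, or 60 mg QD", a threefold spread of starting doses within each arm, and much of the taper dose is given in the first weeks. A single group mean will therefore lie below what a high-dose starter has already taken by an early visit. Replacing that subject's total with the mean deletes recorded steroid. Because V2 counts all observed CS, including escape CS, a subject who flares and then withdraws can exceed the mean sooner still.

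At stake is the credibility of the check on missing data for an alpha-controlled endpoint. Some of the values ranked by the van Elteren test would contradict data already in the database.

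**Working it through.** The plan gives no figure for this analysis, so there is none to reproduce.

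**Inputs.** Weekly doses come from Protocol Appendix E, including the columns headed "Blinded 26-Wk Corticosteroid* Taper". Each row counts as 7 days, with the Baseline row as the first week. The documents do not give the mix of starting doses, so it is assumed: equal (20% each), mostly low (40/30/15/10/5% for 20/30/40/50/60 mg) or mostly high (the reverse). All subjects are taken to be on taper with no escape CS.

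**Scheduled totals** (7 × sum of daily doses, mg):

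| Start | 20 | 30 | 40 | 50 | 60 |
|---|---|---|---|---|---|
| 26-week taper | 945 | 1,330 | 1,855 | 2,205 | 2,625 |
| 52-week taper | 2,212 | 2,597 | 3,122 | 3,472 | 3,892 |

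**Equal-mix means.** 26-week: 8,960 / 5 = 1,792 mg. 52-week: 15,295 / 5 = 3,059 mg. One 10% step is (3,059 − 1,792) / 10 = 126.7 mg.

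**When the running total passes a mean (equal mix).**
- Upadacitinib, own-group mean: week 7 for a 60 mg start (7 × (60+50+40+35+30+25+20) = 1,820 mg), week 11 for 50 mg, week 20 for 40 mg. Starts of 20 and 30 mg never pass it.
- Placebo, own-group mean: weeks 24, 32 and 44 for 60, 50 and 40 mg.
- Placebo, upadacitinib mean: weeks 7, 10, 14, 20 and 27 for 60, 50, 40, 30 and 20 mg.

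**Example.** A 60 mg starter on the 26-week taper who withdraws at Week 12 has received 2,226 mg. The own-group end assigns 1,792 mg, a loss of 434 mg. The 30% step (1,792 + 3 × 126.7 = 2,172 mg) is still too low; the 40% step (2,299 mg) is not. At the placebo-mean end no on-taper upadacitinib subject is above the imputed value under any of the three mixes (maximum 2,625 mg against means of 2,674 to 3,437 mg).

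**Visit-specific means do not remove the problem.** The same starter has 1,925 mg by Week 8, but the equal-mix upadacitinib mean at Week 12 is 1,515 mg.

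**Sensitivity to the assumptions.** The means are 1,407 and 2,674 mg with the mostly-low mix, and 2,170 and 3,437 mg with the mostly-high mix. The 60 mg upadacitinib starter then passes the own-group mean in week 5 or week 12. Dropping the Baseline row gives the same range (week 8 with an equal mix).

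**Effect on the test.** This was simulated with assumptions that are not in the documents: equal dose mix, 10 to 20% study withdrawal, with and without escape CS, and the rule read as Week 52 group means. About 14 to 39% of withdrawn subjects were imputed below their observed dose. At 10% withdrawal, mean Z at the adverse end was −11.7 under the rule as written and −13.9 with only the increment imputed (no escape), or −7.7 and −8.3 (with escape). At the own-group end the two rules barely differed (for example −14.75 and −14.80).

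**The case against.** **The wording may mean interval dose.** SAP 9.4.3 speaks of a value at each visit. If that is the dose taken since the previous visit, nothing impossible arises. But the text names mean cumulative exposure as both anchors and gives no step that adds intervals to the observed total, so this reading has to be supplied by the reader.

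**Low-dose starters.** A reader might infer that giving 1,792 mg to a 20 mg starter, whose schedule totals 945 mg, is equally impossible. It is not. Protocol 5.5 and 5.8 leave CS to the investigator once study drug stops or escape begins, so a total above schedule can occur and is a legitimate adverse assumption.

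**Direction.** A reader might infer that the rule manufactures robustness for upadacitinib, or that its p-values say nothing about withdrawal. The documents do not support either. Crediting high-dose upadacitinib subjects with too little steroid does favour upadacitinib, but only at and near the own-group end, where the simulated Z hardly moved. Pulling placebo subjects down toward the upadacitinib mean works against upadacitinib, so the adverse end is too harsh rather than too lenient.

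**Scope.** The rule covers withdrawal from the study only. Protocol 5.5 and 5.6 keep subjects who merely stop study drug under follow-up with later CS recorded, and V2 uses those data.

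**Anchors.** The actual group means will include escape CS, so 1,792 and 3,059 mg are illustrative figures for subjects on taper.

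The last four points limit the finding. None of them supplies the missing floor.

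**Conclusion.** The rule as written allows imputed totals below observed totals and should be corrected. With an equal mix and no escape CS, an upadacitinib 60 mg starter is exposed to this from week 7 (weeks 5 to 12 across the assumed mixes). Placebo subjects are exposed at the upadacitinib-mean end from weeks 7 to 27, depending on starting dose. For upadacitinib subjects the error is confined to the own-group end and the steps near it. For placebo subjects it can occur anywhere on the range.

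The consequence is limited to one sensitivity analysis. A reader might infer that the V2 result itself is compromised, but the main van Elteren test uses observed data and the alpha path does not depend on the tipping point. The documents give neither a study-withdrawal rate nor a starting-dose mix, so the number of subjects affected cannot be computed.

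**What to change.** In SAP 9.4.3, keep each withdrawn subject's observed cumulative dose and impute only the increment from withdrawal to Week 52. Move that increment in 10% steps from the own-group mean increment to the other-group mean increment over the same interval. Compute both within the baseline CS dose stratum already used in the analysis (> 30 mg, ≤ 30 mg). Five starting-dose levels would leave about 105 / 5 = 21 subjects per cell in the smaller arms, so the existing two strata are the practical choice. If interval doses were intended all along, say so and state that they are added to the observed total.

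For the example above (equal mix of 40, 50 and 60 mg in the upper stratum, Week 12 to Week 52):
- upadacitinib increment: (294 + 343 + 399) / 3 = 345 mg
- placebo increment: (1,400 + 1,470 + 1,540) / 3 = 1,470 mg
- imputed total: 2,226 + 345 = 2,571 mg up to 2,226 + 1,470 = 3,696 mg, never below the dose received.

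The cost is SAP wording and modest programming of one sensitivity analysis. The downside is that the tipping point may look less severe at the adverse end, so the SAP should give the reason for the change.
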